11 PROCEDURES AND INSTRUCTIONS (ADMINISTRATIVE PROCEDURES)

11.1 Changes to the Protocol

Any change to the protocol requires a written protocol amendment or administrative change that must be approved by the sponsor before implementation. Amendments specifically affecting the safety of subjects, the scope of the investigation, or the scientific quality of the study require submission to health or regulatory authorities as well as additional approval by the applicable IRBs/IECs. These requirements should in no way prevent any immediate action from being taken by the investigator, or by the sponsor, in the interest of preserving the safety of all subjects included in the study. If the investigator determines that an immediate change to or deviation from the protocol is necessary for safety reasons to eliminate an immediate hazard to the subjects, the sponsor's medical monitor and the IRB/IEC for the site must be notified immediately. The sponsor must notify the health or regulatory authority as required per local regulations.

Protocol amendments that affect only administrative aspects of the study may not require submission to health or regulatory authority or the IRB/IEC, but the health or regulatory authority and IRB/IEC (or if regionally required, the head of the medical institution) should be kept informed of such changes as required by local regulations. In these cases, the sponsor may be required to send a letter to the IRB/IEC and the Competent Authorities (or, if regionally required, the head of the medical institution) detailing such changes.

11.2 Adherence to the Protocol

The investigator will conduct the study in strict accordance with the protocol (refer to ICH E6, Section 4.5).

11.3 Monitoring Procedures

The sponsor's/CRO's CRA will maintain contact with the investigator and designated staff by telephone, letter, or email between study visits. Monitoring visits to each site will be conducted by the assigned CRA as described in the monitoring plan. The investigator (or if regionally required, the head of the medical institution) will allow the CRA to inspect the clinical, laboratory, and pharmacy facilities to assure compliance with GCP and local regulatory requirements. The CRFs and subject's corresponding original medical records (source documents) are to be fully available for review by the sponsor's representatives at regular intervals. These reviews verify adherence to study protocol and data accuracy in accordance with local regulations. All records at the site are subject to inspection by the local auditing agency and to IRB/IEC review.

In accordance with ICH E6, Section 1.52, source documents include, but are not limited to, the following:

- Clinic, office, or hospital charts

- Copies or transcribed health care provider notes that have been certified for accuracy after production
- Recorded data from automated instruments such as IxRS, x-rays, and other imaging reports (eg, sonograms, CT scans, magnetic resonance images, radioactive images, ECGs, rhythm strips, EEGs, polysomnographs, pulmonary function tests) regardless of how these images are stored, including microfiche and photographic negatives
- Pain, quality of life, or medical history questionnaires completed by subjects
- Records of telephone contacts
- Diaries or evaluation checklists
- Drug distribution and accountability logs maintained in pharmacies or by research personnel
- Laboratory results and other laboratory test outputs (eg, serum or urine pregnancy test result documentation and urine dip-sticks)
- Correspondence regarding a study subject's treatment between physicians or memoranda sent to the IRBs/IECs
- CRF components (eg, questionnaires) that are completed directly by subjects and serve as their own source

11.4 Recording of Data

A CRF is required and must be completed for each subject by qualified and authorized personnel. All data on the CRF must reflect the corresponding source document, except when a section of the CRF itself is used as the source document. Any correction to entries made on the CRF must be documented in a valid audit trail where the correction is dated, the individual making the correction is identified, the reason for the change is stated, and the original data are not obscured. Only data required by the protocol for the purposes of the study should be collected.

The investigator must sign each CRF. The investigator will report the CRFs to the sponsor and retain a copy of the CRFs.

11.5 Identification of Source Data

All data to be recorded on the CRF must reflect the corresponding source documents. For the following item(s), the data recorded directly on the CRF are to be considered source data:

- Study treatment compliance (eg, the reason for dose reduction).
- Discontinuation information.
- Sampling date and time for drug concentration.
- Sampling date and time for the clinical laboratory test.
- Comments and other information on AEs (eg, severity, relationship to study treatment, outcome)

11.6 Retention of Records

The circumstances of completion or termination of the study notwithstanding, the investigator (or if regionally required, the head of the medical institution or the designated representative) is responsible for retaining all study documents, including but not limited to the protocol, copies of CRFs, the Investigator's Brochure, and regulatory agency registration documents (eg, Form FDA 1572), ICFs, and IRB/IEC correspondence). The site should plan to retain study documents, as directed by the sponsor, for at least 2 years after the last approval of a marketing application in an ICH region and until there are no pending or contemplated marketing applications in an ICH region or at least 3 years have elapsed since the formal discontinuation of clinical development of the investigational product.

It is requested that at the completion of the required retention period, or should the investigator retire or relocate, the investigator contact the sponsor, allowing the sponsor the option of permanently retaining the study records.

11.7 Auditing Procedures and Inspection

In addition to routine monitoring procedures, the sponsor's Clinical Quality Assurance department conducts audits of clinical research activities in accordance with the sponsor's SOPs to evaluate compliance with the principles of ICH GCP and all applicable local regulations. If a government regulatory authority requests an inspection during the study or after its completion, the investigator must inform the sponsor immediately.

11.8 Handling of Study Drug

All study drug will be supplied to the PI (or a designated pharmacist) by the sponsor. Drug supplies must be kept in an appropriate secure area (eg, locked cabinet) and stored according to the conditions specified on the drug labels. The investigator (or a designated pharmacist) must maintain an accurate record of the shipment and dispensing of the study drug in a drug accountability ledger, a copy of which must be given to the sponsor at the end of the study. An accurate record of the date and amount of study drug dispensed to each subject must be available for inspection at any time. The CRA will visit the site and review these documents along with all other study conduct documents at appropriate intervals once study drug has been received by the site.

All drug supplies are to be used only for this study and not for any other purpose. The investigator (or site personnel) must not destroy any drug labels or any partly used or unused drug supply before approval to do so by the sponsor. At the conclusion of the study and as appropriate during the study, the investigator (or a designated pharmacist) will return all used and unused drug containers, drug labels, and a copy of the completed drug disposition form to the sponsor's CRA or designated contractor or, when approval is given by the sponsor, will destroy supplies and containers at the site.

11.9 Publication of Results

All manuscripts, abstracts, or other modes of presentation arising from the results of the study must be reviewed and approved in writing by the sponsor in advance of submission pursuant to the terms and conditions set forth in the executed Clinical Trial Agreement between the sponsor/CRO and the institution/investigator. The review is aimed at protecting the sponsor's proprietary information existing either at the date of the commencement of the study or generated during the study.

The detailed obligations regarding the publication of any data, material results, or other information generated or created in relation to the study shall be set out in the agreement between each investigator and the sponsor or CRO, as appropriate.

11.10 Disclosure and Confidentiality

The contents of this protocol and any amendments and results obtained during the study should be kept confidential by the investigator, the investigator's staff, and the IRB/IEC and will not be disclosed in whole or in part to others, or used for any purpose other than reviewing or performing the study, without the written consent of the sponsor. No data collected as part of this study will be used in any written work, including publications, without the written consent of the sponsor. These obligations of confidentiality and non-use shall in no way diminish such obligations as set forth in either the Confidentiality Agreement or Clinical Trial Agreement executed between the sponsor/CRO and the institution/investigator.

All persons assisting in the performance of this study must be bound by the obligations of confidentiality and non-use set forth in either the Confidentiality Agreement or Clinical Trial Agreement executed between the institution/investigator and the sponsor/CRO.

11.11 Discontinuation of Study

The sponsor reserves the right to discontinue the study for medical reasons or any other reason at any time. If a study is prematurely terminated or suspended, the sponsor will promptly inform the investigators/institutions and regulatory authorities of the termination or suspension and the reason(s) for the termination or suspension. The IRB/IEC will also be informed promptly and provided the reason(s) for the termination or suspension by the sponsor or by the investigator/institution, as specified by the applicable regulatory requirement(s).

The investigator reserves the right to discontinue the study should his/her judgment so dictate. If the investigator terminates or suspends a study without prior agreement of the sponsor, the investigator should inform the institution where applicable, and the investigator/institution should promptly inform the sponsor and the IRB/IEC and provide the sponsor and the IRB/IEC with a detailed written explanation of the termination or suspension. Study records must be retained as noted above.

11.12 Subject Insurance and Indemnity

The sponsor will provide insurance for any subjects participating in the study in accordance with all applicable laws and regulations.

12 APPENDICES

Appendix 1 Anaplastic Thyroid Cancer Tumor-Node-Metastasis Staging System

The TNM Staging System (tumor-node-metastasis) is the most widely used system for cancer staging in the world. Staging of ATC in this clinical study will be based on the article by [Smallridge et al, 2012](#), entitled “American Thyroid Association Guidelines for Management of Patients with Anaplastic Thyroid Cancer.”

Primary Tumor	
T4a	Intrathyroidal
T4b	Extrathyroidal
Regional Nodes ^a	
Nx	Regional lymph nodes cannot be assessed
N0	No regional lymph node metastasis
N1	Regional lymph node metastasis
N1a	Metastasis to Level VI (pretracheal, paratracheal, and prelaryngeal/Delphian lymph nodes)
N1b	Metastasis to unilateral, bilateral, or contralateral cervical or superior mediastinal lymph nodes
Distant Metastasis	
MX	Distant metastasis cannot be assessed
M0	No distant metastasis
M1	Distant metastasis

Anaplastic Thyroid Cancer			
Stage Group	T Stage	N Stage	M Stage
IVA	T4a	N0	M0
IVB	T4b	Any N	M0
IVC	Any T	Any N	M1
a. Regional nodes are the central compartment, lateral cervical, and upper mediastinal lymph nodes.			

Appendix 2 Overview of RECIST v1.1 for Evaluation of Tumors Response

Tumor response assessments in this clinical study will use RECIST v1.1 guidelines based on the article by [Eisenhauer, et al., 2009](#), entitled “New response evaluation criteria in solid tumours: Revised RECIST guideline (version 1.1),” with the exception that chest disease may not be followed using chest x-ray and must be assessed with CT. This appendix contains an overview of the RECIST v1.1 guidelines.

Baseline Tumor Assessment

Subjects are required to have measurable disease, defined as the presence of at least 1 measurable lesion, to be eligible for entry into the study. Measurable and nonmeasurable lesions are defined as:

Measurable lesions:

Tumor lesions: Must be accurately measured in at least 1 dimension (longest diameter in the plane of measurement is to be recorded) with a minimum size of:

10 mm by CT scan (CT scan slice thickness no greater than 5 mm)

10 mm caliper measurement by clinical exam (lesions which cannot be accurately measured with calipers should be recorded as nonmeasurable)

Malignant lymph nodes: To be considered pathologically enlarged and measurable, a lymph node must be >15 mm in short axis when assessed by CT scan (CT scan slice thickness recommended to be no greater than 5 mm). At baseline and in follow-up, only the short axis will be measured and followed.

MRI may be substituted for contrast enhanced CT for some sites, but not lung. The minimum size for measurability is the same as for CT (10 mm) as long as the scans are performed with slice thickness of 5 mm and no gap. In the event the MRI is performed with thicker slices, the size of a measurable lesion at baseline should be 2 times the slice thickness. In the event there are interslice gaps, this also needs to be considered in determining the size of measurable lesions at baseline.

Lytic bone lesions or mixed lytic-blastic lesions, with identifiable soft tissue components, that can be evaluated by cross-sectional imaging techniques such as CT or MRI can be considered as measurable lesions if the soft tissue component meets the definition of measurability.

A lesion located in a previously irradiated area, or in an area previously subjected to any locoregional therapy, will be considered measurable only if there has been a documented increase in lesion size subsequent to prior treatment but before study entry.

Clinical lesions: Clinical lesions will only be considered measurable when they are superficial and >10 mm diameter as assessed using calipers (eg, skin nodules). For the case of skin lesions, documentation by color photography including a ruler to estimate the size of

the lesion is suggested. When lesions can be evaluated by both clinical exam and imaging, imaging evaluation should be undertaken since it is more objective and may also be reviewed at the end of the study.

Nonmeasurable lesions: All other lesions, including small lesions (longest diameter < 10 mm or pathological lymph nodes with a short axis of ≥ 10 mm to < 15 mm short axis), lesions that cannot be accurately measured with calipers, and truly nonmeasurable lesions: leptomeningeal disease, ascites, pleural or pericardial effusion, inflammatory breast disease, lymphangitic involvement of skin or lung, abdominal masses/abdominal organomegaly identified by PE that is not measurable by reproducible imaging techniques. Lymph nodes with a short axis <10 mm are considered nonpathological and should not be recorded or followed.

Simple cysts (cystic lesions) will not be considered malignant, and will be neither measurable nor nonmeasurable. Cystic lesions believed to be metastases may be considered measurable if they meet the general definition of measurability, but noncystic lesions are preferred as target lesions.

All baseline tumor evaluations should be performed as closely as possible to the start of treatment and never more than 4 weeks before the first dose of study treatment.

Methods of Tumor Measurement

The same imaging modality and the same technique (including use or nonuse of oral and IV contrast) should be used to characterize each identified and reported lesion at Baseline/Screening and at reassessment time points during the study. All measurements should be taken and recorded in metric notation, using calipers if clinically assessed.

Computed tomography and MRI are the best currently available and reproducible methods to measure target lesions selected for response assessment. Computed tomography should be performed with slices of 5 mm or less in thickness (as a general rule, lesion diameter should be no less than double the slice thickness). This applies to tumors of the chest, abdomen, and pelvis. Magnetic resonance imaging is also acceptable in certain conditions (eg, for body scans). A CT of the chest without contrast is preferred over MRI.

Bone scans, positron emission tomography (PET) scan, or plain films are not sufficient to measure bone lesions and document objective response but may be used to confirm the presence or disappearance of such lesions. Bone scans should be performed using ^{99m}Tc -technetium-labeled polyphosphonate scintigraphy, whole body bone MRI, or ^{18}F -NaF-PET.

Chest x-rays should not be used for baseline assessment of the chest or for follow-up of known lesions. Chest CT should be used.

Ultrasound should not be used to measure tumor lesions.

Endoscopy and laparoscopy should not be used to measure tumor lesions.

Documentation of "Target" and "Nontarget" Lesions

Lesions are evaluated and classified at Baseline as either target or nontarget and all are then followed throughout the study.

Target Lesions:

Target lesions are all measurable lesions up to a maximum of 2 lesions per organ and 5 lesions in total, representative of all involved organs. Target lesions should be selected on the basis of their size (those with the longest diameters) and their suitability for accurate repeated measurements.

The short axis (≥ 15 mm) of any lymph nodes selected as target lesions at Baseline will be measured and recorded at each evaluation time point, even if the nodes become nonpathological (short axis < 10 mm).

The sum of the diameters of all target lesions (longest for non-nodal lesions, short axis for nodal lesions) will be calculated at Baseline and reported as the baseline sum diameter. This baseline sum of diameters will be used as the reference by which to characterize objective tumor response.

Target Lesions Too Small To Measure:

Lesions that become too small to measure during treatment should be assigned a default measurement of either 0 mm (if the investigator believes the lesion has disappeared) or 5 mm (if the lesion is believed to be present and is faintly visible).

Target Lesions That Split or Coalesce:

If a non-nodal target lesion fragments during treatment, the longest diameters of each fragment should be added together to calculate the total sum for that lesion. When lesions coalesce, a plane between them may be maintained that would aid in obtaining maximal diameter measurements for each individual lesion. If the lesions are no longer separable, the vector of the longest diameter in this instance should be the maximal longest diameter for the coalesced lesion.

Nontarget Lesions:

All other lesions (or sites of disease) should be identified as nontarget lesions and should also be recorded at Baseline. Measurements of these lesions are not required, but the presence or absence of each should be noted throughout Follow-up.

New Lesions:

The finding of a new lesion should be unequivocal (ie, not attributable to a change in scanning technique or imaging modality, and not thought to represent something other than a tumor). If a possible new lesion is equivocal, treatment and radiographic evaluation should continue per this protocol until confirmation of PD or until additional scans confirm the presence of a new lesion. In such a case, the date of progression will be the date of the initial scan.

A lesion identified on a Follow-up study of an anatomical location not studied as Baseline will be considered a new lesion.

Scanning with FDG-PET may be employed as a complement to CT scanning in the assessment of PD. A negative FDG-PET scan at Baseline with a positive scan during the study will be evidence of PD. If there is no FDG-PET scan at Baseline and a positive FDG-PET scan during the study, it will be considered evidence of PD if the positive FDG-PET corresponds to a new site of disease confirmed by CT scan. A positive postbaseline FDG-PET result corresponding to a pre-existing site of disease with no radiographic evidence of progression will not be considered evidence of PD.

Evaluation of Response for an Individual Assessment Time Point

To determine tumor response, the sum of all target lesions is calculated at Baseline and at each subsequent assessment time point (ie, every 6 weeks until progression in this study). Each response parameter (target, nontarget, and new lesions) will be reported independently at each radiographic reading as shown in [Table 1](#) for target lesions and [Table 2](#) for nontarget lesions. The investigator will then make a determination of OR for each assessment time point based on a composite evaluation of target, nontarget, and new lesions, as shown in [Table 3](#).

Table 1 Evaluation of Target Lesions

Complete Response (CR)	Disappearance of all target lesions. All pathological lymph nodes (whether target or nontarget) must have a reduction in their short axis to <10 mm.
Partial Response (PR)	At least a 30% decrease in the sum of the LD of target lesions, taking as reference the Baseline sum diameters
Progressive Disease (PD)	At least a 20% increase in the sum of the LD of target lesions, taking as reference the smallest sum LD recorded at Baseline or during treatment. The sum must also have an absolute increase of ≥ 5 mm.
Stable Disease (SD)	Neither sufficient shrinkage to qualify for PR nor sufficient increase to qualify for PD, taking as reference the smallest sum LD since the treatment started
Not Evaluable (NE)	No imaging/measurement done at all or only on a subset of lesions at a particular time point; a target lesion at Baseline that is subsequently not measured or that is unable to be evaluated. Includes scans that are not performed at a specified time point to evaluate the target lesion(s).

Table 2 Evaluation of Nontarget Lesions

Complete Response (CR)	Disappearance of all nontarget lesions. All lymph nodes <10 mm (short axis)
Non-CR/Non-PD	Persistence of 1 or more nontarget lesion(s)
Progressive Disease (PD)	Unequivocal progression (substantial worsening in nontarget disease such that overall tumor burden has increased sufficiently to warrant discontinuation of therapy); unequivocal progression of existing nontarget lesions ^a
Not Evaluable (NE)	A nontarget lesion at Baseline that is subsequently not measured or that is unable to be evaluated

a: Although a clear progression of "nontarget" lesions only is exceptional, in such circumstances, the opinion of the site radiologist should prevail.

Table 3 Overall Response at Each Assessment Time Point for Subjects with Target (\pm Nontarget) Disease

Target Lesions	Nontarget Lesions	New Lesions	Overall Response
CR	CR	No	CR
CR	Non-CR/Non-PD	No	PR
CR	Not evaluated	No	PR
PR	Non-PD or not all evaluated	No	PR
SD	Non-PD or not all evaluated	No	SD
Not all evaluated	Non-PD	No	NE
PD	Any	Yes or No	PD
Any	PD	Yes or No	PD
Any	Any	Yes	PD

CR = complete response, NE = not evaluable, PD = disease progression, PR = partial response, SD = stable disease.

Subjects with a global deterioration of health status requiring discontinuation of treatment without objective evidence of PD at that time point assessment should be classified as having "symptomatic deterioration." Every effort should be made to document objective progression after discontinuation of treatment.

In some circumstances, it may be difficult to distinguish residual disease from normal tissue. When the evaluation of CR depends on this determination, it is recommended that the residual lesion be investigated (fine needle aspirate/biopsy) before assigning a status of CR.

Evaluation of Best Overall Response (BOR) and Confirmation of Response

The best overall response is the best response recorded from the start of the treatment until disease progression/recurrence (taking as reference for PD the smallest measurements [nadir] recorded since the treatment started). In general, the subject's best response assignment will

depend on the achievement of both measurement and confirmation criteria as shown in [Table 4](#).

Confirmation: To be assigned a BOR of PR or CR, changes in tumor measurements must be confirmed by repeat assessments that should be performed no less than 4 weeks after the criteria for response are first met. In this study, a bone scan should be done within 1 week after the CR confirmatory scanning time point to exclude new bone metastases.

- The main goal of confirmation of the PR or CR objective response is to avoid overestimating the response rate.
- In the case of SD, follow-up measurements must have met the SD criteria at least once after study entry at a minimum interval of 5 weeks for this protocol.

Table 4 Best Overall Response With Confirmation

Unconfirmed response (First Time Point)	Confirmatory Response (Subsequent Time Point)	Best Overall Response of:
CR	CR	CR
CR	PR	SD, PD or PR ^a
CR	SD	SD or PD ^b
CR	PD	SD or PD ^b
CR	NE	SD or NE ^c
PR	CR	PR
PR	PR	PR
PR	SD	SD
PR	PD	SD ^b
PR	NE	SD ^c
NE	NE	NE

BL = baseline, CR = complete response, NE = not evaluable, PD = disease progression, PR = partial response, SD = stable disease.

a: If a CR is truly met at the first time point, then any reappearance of disease seen at a subsequent time point (including disease meeting PR criteria relative to BL) makes the disease PD at that time point.

b: Classify response as SD, provided that confirmatory scan a minimum of 5 weeks later is still "SD." Otherwise, response will be classified as PD.

c: Classify response as SD, provided that confirmatory scan a minimum of 5 weeks later is still "SD." Otherwise, response will be classified as NE.

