9.7.1.1.3 EXPLORATORY ENDPOINTS

- CBR is the proportion of subjects who have best overall response of CR or PR or durable SD. Stable disease must be achieved at ≥ 23 weeks after first lenvatinib administration to be considered durable SD.
- DCR is the proportion of subjects who have best overall response of CR, PR or SD. Stable disease must be achieved at ≥ 5 weeks after the first lenvatinib administration to be considered BOR.
- DOR is defined as the time from the date that the criteria are met for CR or PR, whichever is recorded first, to the date that PD is objectively documented or death, whichever occurs first.
- Evaluate the association of tumor and blood biomarkers with clinical outcomes, including efficacy.

All above primary, secondary and exploratory endpoints based on tumor measurement will be assessed according to RECIST 1.1.

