### 5.1.3 Exploratory Endpoints

- **Clinical benefit rate (CBR)** is the proportion of subjects who have the best overall response (confirmed) of CR or PR or durable SD. A stable disease (SD) must be at  $\geq 5$  weeks after the first study dose. A durable SD is a subset of SD with the duration of  $\geq 23$  weeks after the first study dose.
- **Disease control rate (DCR)** is the proportion of subjects who have the best overall response (confirmed) of CR, PR or SD.
- **Duration of response (DOR)** is defined as the time from the first objective response (i.e., the initial CR or PR that was confirmed) to the first documented disease progression or death. This endpoint is just defined for the subjects who had confirmed response during study.
- Evaluate the association of tumor and blood biomarkers with clinical outcomes, including efficacy.

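### Appendix 2 Table 4: footnote b cannot be met in the rows that end in PD, and footnote c is ambiguous in the NE rows, so best overall response and exploratory DCR depend on how they are read

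*Protocol*

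**What the plan says.** Protocol Appendix 2, Table 4, gives BOR from a first time point and a second column headed "Confirmatory Response (Subsequent Time Point"). The rows that matter are:

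- CR→SD and CR→PD: the cell allows SD or PD, with footnote b.
- PR→PD: the cell prints SD alone, with footnote b.
- CR→NE: the cell allows SD or NE, with footnote c.
- PR→NE: the cell prints SD alone, with footnote c.

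Both footnotes give SD "provided that confirmatory scan a minimum of 5 weeks later is still" SD. Footnote b ends "Otherwise, response will be classified as PD"; footnote c ends "Otherwise, response will be classified as NE".

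The SD minimum is set differently in three other places. The bullet above Table 4 says that "follow-up measurements must have met the SD criteria at least once after study entry at a minimum interval of 5 weeks for this protocol". Protocol 9.7.1.1.3, under DCR, says "Stable disease must be achieved at ≥ 5 weeks after the first lenvatinib administration to be considered BOR". SAP 5.1.3 also counts 5 weeks from the first study dose, and its DCR "is the proportion of subjects who have the best overall response (confirmed) of CR, PR or SD". SAP 5.1 takes BOR from the investigators under RECIST 1.1. SAP section 7, which lists changes to the planned analyses, does not mention the point.

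**The concern.** A footnote should say when the value in its cell applies. Here footnote b sets a condition that the row itself rules out, so a reader must follow either the cell or the footnote. The two give different BORs for the same subject, and DCR counts one and not the other.

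The footnotes also measure a different interval from the rest of the plan. They count 5 weeks forward to a later scan that must read SD. The bullet, protocol 9.7.1.1.3 and SAP 5.1.3 count from study entry or first dose and ask for no second SD scan. About 20 centers assign BOR, so the clash could be settled in different ways within one trial. In a disease this aggressive, a response followed by progression at the next scan is a plausible pattern.

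**Working it through.** **Plan's own figure.** The documents give no DCR target, hypothesis or power. The nearest figure is the ORR power of 0.932 (57 evaluable subjects, 10% versus 27%, 1-sided 0.025). The smallest count r with P(X ≥ r | 57, 0.10) ≤ 0.025 is 11, with exact alpha 0.0242. P(X ≥ 11 | 57, 0.27) = 0.9321, which reproduces it. The footnotes do not enter: an unconfirmed CR or PR followed by PD or NE is not a confirmed response under either reading.

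**Scan timing.** From protocol 9.5.1.3.1 (every 6 weeks, ±1 week), the first scan falls at weeks 5–7 and the second at weeks 11–13. The gap runs from 11 − 7 = 4 to 13 − 5 = 8 weeks. A scheduled first scan is therefore always at least 5 weeks after first dose.

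**Rows compared.** The last column assumes that an unconfirmed CR or PR counts as at least SD, as Table 4's own SD entries imply.

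| First → next scan | Table 4 cell | Footnote read literally | SD minimum counted from first dose |
|---|---|---|---|
| CR → PD | SD or PD (b) | PD | SD |
| PR → PD | SD (b) | PD | SD |
| CR → NE | SD or NE (c) | NE, unless a later SD scan counts | SD |
| PR → NE | SD (c) | NE, unless a later SD scan counts | SD |
| CR → SD | SD or PD (b) | SD if scans are ≥5 weeks apart; PD at a 4-week gap (weeks 7 and 11) | SD |
| PR → SD | SD (no footnote) | SD | SD |

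**Ordering check.** SD at week 6 then PD at week 12 meets the bullet above the table, so BOR is SD. PR at week 6 then PD at week 12 is PD under literal footnote b. The better first scan gives the worse BOR.

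**Direction and size.** Compared with the first-dose rule, the literal footnotes only move subjects out of SD, so DCR can only fall. Each such subject moves DCR by 1/57 = 1.75 percentage points in the planned evaluable set. Subjects with an earlier SD scan at 5 weeks or later are not affected, because that scan already secures SD. The documents give no basis for the number affected. Purely for scale, an assumed 1, 3 or 5 subjects would give 1/57 = 1.8, 3/57 = 5.3 or 5/57 = 8.8 points.

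**The case against.** Four points on the other side have force.

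- **DCR may not be understated at all.** A reader might infer that the plan understates DCR. The documents do not support that as a fact. It follows only if sites or programmers let the footnotes override the printed SD entries. SAP 5.1 takes BOR from investigators, and SAP section 9 puts derivation rules in separate documents not available here.
- **Footnote c is not defective in the same way.** A reader might extend the point to the NE rows. But NE does not end assessment: scanning continues until progression is documented, so PR→NE→SD can satisfy footnote c if its confirmatory scan is the one after the NE. The column heading points the other way, so the footnote is ambiguous but not impossible to meet. The PD rows allow no such reading.
- **Protocol 9.7.1.1.3 and SAP 5.1.3 do not themselves make an unconfirmed PR into SD.** They set a minimum time for SD. Table 1 of Appendix 2 defines target-lesion SD as excluding shrinkage that reaches PR. The contradiction over PR→PD is therefore inside Table 4, between cell and footnote. The other sections differ from the footnotes only in where the 5 weeks start and in not asking for a second SD scan.
- **The endpoint is exploratory.** DCR carries no hypothesis or threshold, and footnote b can be met in one of its rows, CR→SD.

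All four stand and limit the point. None removes the conflict in the two PD rows.

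**Conclusion.** Table 4 is wrong as written in the CR→PD and PR→PD rows, and unclear in the CR→NE and PR→NE rows. The SAP does not settle either. If footnote b is applied literally, exploratory DCR can only fall, by 1.75 points per affected subject. That figure assumes the planned 57 evaluable subjects; SAP 5.4.3 also allows these analyses in the full analysis set, where the step per subject would be smaller if that set is larger. How many subjects would be affected, and whether anyone would apply the footnote literally, cannot be known from the documents.

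ORR and its power, the interim responder count, PFS and OS are unaffected. CBR is touched only where the SD in question lasts at least 23 weeks. This is a minor, inexpensive correction to a stated classification rule.

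**What to change.** Replace footnotes b and c with one rule: SD, provided an assessment of SD or better was made at least 5 weeks after the first dose; otherwise PD (footnote b) or NE (footnote c). State the same rule in the SAP's BOR derivation, and say there whether the word confirmed in the DCR definition applies to SD.

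The rule should refer to any assessment of SD or better, not to the first time point alone. Earlier scans are allowed when clinically indicated, so a CR at week 4 followed by SD at week 10 is possible. A rule tied to the first scan would class that subject as PD, although the week-10 scan meets the SD minimum everywhere else in the plan. Under the proposed rule the later SD scan counts. PR at week 4 followed by PD at week 10 would still be PD.

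The cost is the wording of two footnotes and a line in the SAP and derivation specification. No sample size, power or schedule changes.
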